### **11.3 Essential Records Retention**

The Investigator should maintain the essential clinical study documents (including CRFs, source documents, clinical drug disposition records, signed subject informed consent forms, AE reports and other regulatory documents) as required by the applicable national regulatory requirements. The Investigator is to take adequate measures to prevent accidental or premature destruction of these documents. In the event of accidental destruction, the Investigator should notify the Sponsor (or an authorized representative) immediately.

Essential clinical study documents will be retained at least two (2) years after the last approval of a marketing application in an ICH region and until there are no pending or contemplated marketing applications in an ICH region OR at least two (2) years have elapsed since the formal discontinuation of clinical development of the investigational product. These documents shall be retained for a longer period, however, if required by the applicable regulatory requirements or by an agreement with the Sponsor (or an authorized representative).

The Investigator is required to notify the Sponsor (or an authorized representative) prior to changing the location or status of any essential clinical study documents. The Sponsor (or an authorized representative) will be responsible for informing the Investigator as to when these documents no longer need to be retained.

### **11.4 Investigator Agreement**

The Investigator is responsible for assuring the proper implementation and conduct of the clinical study including those study-related duties delegated to other appropriately qualified individuals. The Investigator and his/her staff will cooperate with the Sponsor (or an authorized representative) during monitoring and auditing visits to assist with the review of the study data and resolve any discrepancies.

The Investigator will demonstrate due diligence in recruitment and screening of potential study subjects. The enrollment rate should be sufficient to complete the study as agreed with the Sponsor (or an authorized representative). The Sponsor (or an authorized representative) is to be notified of any projected delays, which may impact the completion of the study.

---

The Sponsor retains the right to terminate the clinical study at any time for any reason. In such an event, instructions on the requirements for the discontinuation of subjects will be provided by the Sponsor (or an authorized representative).

---

## **12 SPONSOR OBLIGATIONS**

### **12.1 Protocol Amendments**

Only the Sponsor (or an authorized representative) will make modifications to the clinical study protocol, which will be documented in a written amendment that describes all changes that will be implemented. Protocol amendments will be categorized as either substantial or non-substantial.

Protocol amendments will be considered substantial when the changes have significant impact on:

- The safety of physical or mental integrity of the subjects
- The scientific value of the study
- The conduct or management of the study
- The quality or safety of any investigational medicinal product or control used in the study

Protocol amendments will be considered non-substantial when the changes affect only administrative issues with the conduct of the study, i.e., changes in telephone numbers or addresses.

The Sponsor (or an authorized representative) will be responsible for notifying the appropriate national regulatory authorities in writing of any amendments to the protocol prior to the changes being implemented except in those cases where the changes are necessary to eliminate an immediate hazard to the clinical study subjects.

Substantial amendments will require written approval by the IEC/IRB prior to being implemented by the Investigator at the study site except under those circumstances described previously. Non-substantial amendments will not require approval by the IEC/IRB unless requested by the IEC/IRB.

### **12.2 Study Monitoring**

The study will be monitored by authorized representatives of the Sponsor throughout its duration by means of personal visits to the Investigator's facilities and through other communications (e.g., telephone calls, written correspondence). Monitoring visits will be scheduled at mutually agreeable times periodically throughout the study and at frequency deemed appropriate for the study.

In addition to onsite monitoring the Sponsor may choose a combination of on-site and centralized monitoring. Centralized monitoring is a remote evaluation of accumulating data, performed in a timely manner, supported by appropriately qualified and trained persons (e.g., data managers, biostatisticians).

These visits will be conducted to evaluate the progress of the study, ensure the rights and well-being of the subjects are protected, check that the reported clinical study data are accurate, complete and verifiable from source documents, and the conduct of the study is in compliance with the approved protocol and amendments, GCPs and applicable national regulatory

---

requirements. A monitoring visit will include a review of the essential clinical study documents (regulatory documents, CRFs, source documents, drug disposition records, subject informed consent forms, etc.) as well as discussion on the conduct of the study with the Investigator and staff. The Investigator and staff should be available during these visits to facilitate the review of the clinical study records and resolve/document any discrepancies found during the visit.

### **12.3 Quality Assurance and Quality Control**

As part of the Sponsor's (or an authorized representative's) quality management approach, Quality Assurance department may conduct on-site audits of all aspects of the clinical study either during the study or after the study has been completed.

The clinical study may also be subject to inspection by regulatory authorities (national or foreign) as well as the IECs/IRBs to ascertain that the study is being or has been conducted in accordance with protocol requirements, GCPs, as well as the applicable regulatory requirements.

---

**13 PUBLICATION POLICY**

The data generated by this study are confidential information of the Sponsor. The Sponsor will publicly disclose the study and the study results of all applicable clinical trials following legal and regulatory requirements. The publication policy with respect to the Investigator and study center will be set forth in the Clinical Trial Agreement.

---

**14 INSURANCE**

The Sponsor has taken out a liability insurance, which covers this study as required by local law and/or national regulations and/or ICH guidelines whichever is applicable. Insurance will be covered by the sponsor in accordance to the local regulations.

---

## **16 APPENDICES**

### **16.1 Appendix – Participating Countries’ National Insurance Requirements**

Insurance will be covered by the sponsor in accordance to the local regulations

### **16.3 Appendix –Clinical laboratory(ies) involved in the trial**

The respective local clinical laboratories will be used after site selection.

## 1. ABBREVIATIONS

### 1.1 Standard Abbreviations

AE	Adverse Event
ANCOVA	Analysis of Covariance
BMI	Body Mass Index
CDISC	Clinical Data Standards Consortium
CRF	Case Report Form
CRO	Contract Research Organization
ECG	Electrocardiogram
FA	Full Analysis
GI	Gastrointestinal
HLT	High Level Term
ICH	International Conference on Harmonization
LDQ	Leeds Dyspepsia Questionnaire
LS Mean	Least Square Mean
Max	Maximum
MedDRA	Medical Dictionary for Regulatory Activities
Min	Minimum
N	No
N,n	Number of observations
NA	Not Applicable
NI Margin	Non Inferiority Margin
NRS	Numerical Rating Scale
PI	Principal Investigator
PP	Per Protocol
PPIs	Proton Pump Inhibitors
PT	Preferred Term
QoL	Quality of Life
SAE	Serious Adverse Event
SAP	Statistical Analysis Plan
SAS	Statistical Analysis System
SD	Standard Deviation
SF-NDI	Short Form-Nepean Dyspepsia Index
SOC	System Organ Class
SOP	standard operating procedure
TEAE	treatment-emergent adverse event
TESAE	treatment-emergent serious adverse event
TID	Three times a day
TLF/T,L,F	tables, listings, and figures
UIN	Unique Identification Number
Y	Yes

## **2. INTRODUCTION**

The statistical analysis plan – module 1 & 2 (SAP), produced in accordance with the Abbott standard operating procedures (SOPs) and International Conference on Harmonization (ICH) guidelines, contains a technical elaboration of the principal features of the statistical analyses as described in the protocol of study ITOP-322-0216 final version 1.0 dated 05SEP2023.

Module 1 is primarily restricted to the description of the analysis and reporting of the non-standard data. Module 2 [1] contains the details, including standard definitions and programming instructions, for the analysis and reporting of standard data (disposition, protocol deviation, demographics, medical history, concomitant medication, adverse events, safety laboratory data, vital signs, and safety electrocardiogram data). Module 2 is standard. Any text from Module 2 which is not applicable due to the study design, or otherwise, is specified and revised text is added to Module 1.

Analysis data sets and statistical output will be produced by the Biostatistics project planning and programming department of Tech-observer India, using the SAS® system Version 9.4 or higher.

### **3. SUMMARY OF THE PROTOCOL**

#### **3.1 Overall Study Plan**

This is a Phase 3, randomized, open-label, multicenter, parallel-group, active-controlled study to evaluate the non-inferiority in efficacy of Itopride Hydrochloride 150mg extended release tablet (administered once daily) compared to Itopride Hydrochloride 50mg film coated tablets (administered TID) in subjects with gastrointestinal symptoms caused by gastric dysmotility and delayed gastric emptying, like sensation of bloating, early satiety, postprandial fullness, upper abdominal pain or discomfort, anorexia, heartburn, nausea and vomiting; functional (non-ulcer) dyspepsia or chronic gastritis.

The investigator or designee will explain the study to potentially interested subjects in detail, and if they voluntarily agree to participate in the study, consent will be obtained.  
The study will screen approximately 700 subjects.

Screening will be carried out to evaluate the eligibility criteria. Upper GI endoscopy will be conducted to rule out any organic, structural disease. The upper GI endoscopy report should be within 6 months prior to randomization. If it is > 6 months old, then it will be performed during screening.

After meeting the eligibility criteria, subjects will be enrolled in the study and will be assigned Unique Identification Numbers (UINs) to maintain confidentiality.

After screening, 564 subjects (282 subjects in each arm) will be randomized in a 1:1 ratio to one of the following treatment groups:

- Test group - Itopride Hydrochloride 150 mg extended-release tablets once daily before one of the main meals (preferably the same meal throughout the treatment)
- Active Control group - Itopride Hydrochloride 50 mg film coated tablets 3 times daily before meals.

The study drugs will be administered, as mentioned above, for a period of 8 weeks.

The duration of treatment will be 8 weeks, and the subject follow up will be one week after the end of treatment.

Subjects must stop most drugs which are active on gastric function prior to the study. Rescue medication, i.e. PPIs or antacids, for subjects with persistent symptoms of gastric hypersecretion may be started, after confirmation by the PI, earliest after 4 weeks (visit 3).

#### **3.2 Study Flowchart**

The flowchart of the study can be found in [Appendix 9.1](#).

#### **3.3 Study Objectives**

##### **Primary Objective:**

- To assess the comparable efficacy of Itopride Hydrochloride 150 mg extended-release tablet (administered once daily) and Itopride Hydrochloride 50 mg film coated tablets (administered TID) after 8 weeks' treatment.

**Secondary Objectives:**

- To assess the comparable efficacy of Itopride Hydrochloride 150 mg extended-release tablet (administered once daily) and Itopride Hydrochloride 50 mg film coated tablets (administered TID) after 4 weeks treatment.
- To assess quality of life for the two treatment arms using Disease Specific Quality of Life (Nepean Dyspepsia Index NDI) at baseline and end of treatment
- To assess the symptomatology (sensation of bloating, early satiety, postprandial fullness, upper abdominal pain, or discomfort (epigastric pain, epigastric burning), anorexia (loss of appetite), heartburn, nausea, and vomiting) of the disease in both treatment arms after 4 and 8 weeks of treatment.
- To assess the number of responders of adequate/satisfactory relief from functional dyspepsia symptoms.

**Exploratory Objective:**

- Treatment acceptance by subjects using 5-point Likert scale at the end of treatment

**Safety Objective:**

- To evaluate safety and tolerability in both treatment arms

## 4. STATISTICAL ANALYSIS

Data handling responsibility is of the Clinical Data Management (CDM) team of the tech-observer. The data will be inspected for inconsistencies by performing validation checks. Any inconsistencies found will be resolved by the monitor after contacting the Investigator. When the data in the database are considered clean the database will be made available as SAS® files for statistical analysis.

The Statistical Analysis Plan is prepared by Biostatistics projects Planning and Programming (BPP) team of the Tech-Observer and approved by Abbott before database lock.

The statistical analysis will be done by the BPP team of the tech-observer.

### General Considerations:

Treatment Day:

All assessment Treatment day calculation/consideration refer section 2.3.1 of SAP module 2

Baseline:

For baseline definition refer section 2.3.2 of SAP module 2

Gap Period:

The Gap Period is defined as 7 days. In that case the last administration of study drug occurred on Day 30 relative to the start of treatment, an assessment obtained on Day 33 will be analyzed as part of that treatment.

The default summary statistics for quantitative variables and qualitative variables and decimal point presentation will be followed as per section 2.1 of SAP module 2.

### 4.1 Subject samples

The main subject samples of interest are defined as follows:

- All Subjects Consented subject sample will consist of all subjects who:
  - Gave their informed consent.
- All Subjects Allocated to Treatment subject sample will consist of all subjects who:
  - Were in all subjects consented sample, and
  - Were randomized to treatment.
- The Safety subject sample will consist of all subjects who:
  - Were in all subjects allocated to treatment sample; and
  - Had at least one dose of study medication administered.
- The Full Analysis (FA) subject sample will consist of all subjects who:
  - Were included in the safety sample; and

- Had data for at least one post-baseline assessment of any efficacy measurement.
- The Per Protocol (PP) subject sample will be defined through blind data review and will consist of all subjects who:
  - Were included in the Full Analysis sample; and
  - Did not present any major protocol violation.

## **4.2 Efficacy analysis**

The Full Analysis (FA) and Per Protocol (PP) sample will be used for the analysis of the primary efficacy data. The analysis for the per-protocol sample will be regarded as primary. Full analysis sample will be used for the analysis of the secondary endpoints.

The default summary statistics for quantitative and ordinal variables will be the number of non-missing observations (n), mean, standard deviation (SD), median, minimum (Min) and maximum (Max) for subjects with data.

For qualitative variables, per category the numbers and frequencies of subjects with non-missing data (n, %) will be the default summary presentation, and if appropriate, the number of missing values will be presented.

### **4.2.1 Primary Efficacy Analysis**

- **Change in Leeds Dyspepsia Questionnaire (LDQ) Severity Score between baseline and week 8**

A by-participants data listing will be provided for all subject consented subject sample, which contains data information for Leeds Dyspepsia Questionnaire (LDQ) questionnaire from CRF. LDQ severity score and change in LDQ severity score from baseline will also be listed for all participants.

The primary endpoint is the change in the overall severity of functional dyspepsia between baseline and week 8, as measured by the Leeds Dyspepsia Questionnaire (LDQ) severity score.

The values of Leeds Dyspepsia Questionnaire (LDQ) severity score will be derived as per [section 5.3.1](#).

The actual values at baseline and week 8 and values of change from baseline at week 8 will be summarized using the number of non-missing observations (n), mean, standard deviation (SD), median, minimum (Min) and maximum (Max) by Test group and Active Control group.

The primary endpoint Leeds Dyspepsia Questionnaire (LDQ) severity score will be analyzed using analysis of covariance (ANCOVA) model. The model will include change in the LDQ score as dependent variable and treatment groups, site and LDQ baseline value as covariates. Two-sided 95% confidence intervals will be constructed for the Least Square Mean (LS Mean) differences between Test group and Active Control group. Normal approximation will be assumed for the parametric analyses.

The following sample SAS code pertains to the analysis:

```
proc mixed;  
  class TREATMENT SITE;  
  model CHG = BASE TREATMENT SITE/solution;  
  lsmeans TREATMENT/ stderr pdiff cl alpha=0.05;  
  ods output diffs = DIFFS lsmeans = LSMEANS;  
run;  
*CHG: LDQ change from baseline values  
*BASE: LDQ baseline values
```

Non-inferiority of Test group (Itopride Hydrochloride 150 mg extended-release tablets once daily before one of the main meals) compared to Active Control group (Itopride Hydrochloride 50 mg film coated tablets 3 times daily before meals) will be assessed using Full Analysis (FA) and Per Protocol (PP) subject sample for the entire study population.

The non-inferiority margin is set as 1.75 and thus the null and alternative hypothesis will be stated as follows:

Null Hypothesis:

Test group is inferior to active control group

Alternative Hypothesis:

Test group is non-inferior to active control group

Where,

$\Delta_T$  = Mean change in LDQ score from baseline for Test group

$\Delta_A$  = Mean change in LDQ score from baseline for Active Control group

Non inferiority will be achieved using the lower bound of the 95% confidence interval of the difference between the Test groups and Active Control group. If the lower bound of the 95% confidence interval of the difference between the Test groups and Active Control group is greater than 1.75 (NI-margin), Test group will be declared non-inferior to Active Control group, and the study will be considered a success.

The above analysis will be performed for both the per protocol and the full analysis set. The analysis for the per-protocol set will be regarded as primary.

For the primary PP analysis, the major protocol deviations/violations will be determined before DB lock.

All data points as results of major deviations/violations will be excluded.

Subjects who have taken the rescue medication marked as minor protocol deviation will be included in Per Protocol sample. All data points will be disregarded and considered as missing after the use of rescue medication.

Resulting missing values will be replaced using MI (like a hypothetical strategy in the estimand framework). Replacing missing values by MI will also be done as part of FAS analysis that otherwise includes all observed.

The data will be separated into two subsets based on the treatment groups which will ensure that the imputation process accounts for potential difference between these groups. Complete dataset will be generated using PROC MI and recombine the data set for subsequent analysis. The number of imputed data set should be sufficient to ensure reliable result. PROC MIANALYZE will be used to combine the results of complete dataset results.

The following sample SAS code pertains to the imputation:

```
/* Step 1: Separate data into two subsets based on treatments and Perform Multiple Imputation separately for each group */
```

```
PROC MI DATA=data OUT=imputed_data NIIMPUTE=X (usually considered 5 for data values missing up to 20%) SEED=XXXXXX;
```

```
Class Site;
```

```
VAR var 1 var 2 var3;
```

```
MONOTONE/FCS REG;
```

```
Run;
```

```
/* Use Monotone or FCS regression imputation based on missing values pattern*/
```

```
/* Step 2:
```

```
Re-combine the imputed dataset for each group and Analyze the imputed dataset */
```

```
PROC MIXED DATA=combined;
```

```
CLASS treatment site;
```

```
MODEL chg = base treatment site/SOLUTION;
```

```
LSMEANS treatment/ STDERR PDIFF CL ALPHA=0.05;
```

```
    BY _imputation_ ; /* perform analysis for each imputed dataset */  
    ODS OUTPUT DIFFS = diffs LSMEANS = lsmeans; /*Use the ODS Output tables required  
as per need*/;  
run;  
/* Step 3:  
Pooled the result from multiple imputation */  
ODS OOUTPUT PARAMETERESTIMATES=estimate; /*use the ODS Output tables required  
as per need*/  
PROC MIANALYZE DATA=lsmeans/diffs;  
/* If any By variable is required, use BY option*/  
    MODELEFFECTS estimate;  
    STDERR StdErr;  
Run;
```

In order to test robustness of results following analyses will be performed:

- Leeds Dyspepsia Questionnaire (LDQ) severity score will be analyzed using mixed model repeated measure (MMRM) model for FAS population. No missing values will be imputed for the analysis.
- Leeds Dyspepsia Questionnaire (LDQ) severity score will be analyzed using mixed model repeated measure (MMRM) model for PP population where, missing values will be imputed for the data points not excluded due to deviation will be replaced using MI.
- Leeds Dyspepsia Questionnaire (LDQ) severity score will be analyzed using ANCOVA model for PP population that includes subjects who complete all visits of study as per protocol.

The following sample SAS code pertains to the MMRM analysis:

```
PROC MIXED DATA=data METHOD=REML;  
    CLASS Treatment Site Subject Visit;  
    MODEL aval = base treatment site visit treatment*visit /SOLUTION DDFM=kr;  
    REPEATED Visit/ SUBJECT=Subject TYPE=un; /* If UN is not convergence, follow the  
sequence as TOEP, AR(1) and CS */  
    LSMEANS Treatment*Visit /CL DIFF;  
RUN;
```

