
Change in the overall severity of functional dyspepsia between baseline and week 8, as measured by the Leeds Dyspepsia Questionnaire (LDQ) severity score
 
Secondary endpoint(s):
 
 
• Change in the overall severity of functional dyspepsia between baseline and week 4, as measured by the Leeds Dyspepsia Questionnaire (LDQ) severity score
 
• Disease Specific Quality of Life (Nepean Dyspepsia Index NDI) assessed at baseline and week 8
 
• Change from baseline of NRS 11 score for symptoms (sensation of bloating, early satiety, postprandial fullness, upper abdominal pain or discomfort (epigastric pain, epigastric burning), anorexia (loss of appetite), heartburn, nausea and vomiting) after 4 and 8 weeks of treatment
 
• Responder analysis for adequate/satisfactory relief as assessed by LDQ and/or NRS 11
 
• Treatment acceptance and ease of use assessed by subjects using 5-point Likert scale
 
 
Safety:
 
 
• To evaluate the safety and tolerability of the two treatments by assessing the following safety endpoints: Treatment emergent adverse events (TEAEs) as detected by physical examination, laboratory assessments and vital signs.
 
		

Statistical Methods:
 
Efficacy
 
Primary efficacy:
 
 
• An ANCOVA analysis will be performed with the change in the LDQ score as dependent variable and treatment group, site and LDQ baseline value as additional factors. The difference between the two treatment groups will be calculated for the non-inferiority comparisons, together with a two-sided 95% confidence interval. Non-inferiority will be considered achieved if the lower bound of the 95% confidence interval of the difference between the two groups is greater than 1.75 (NI-margin). Normal approximation will be assumed for the parametric analyses. The primary analysis will be performed for both the per protocol set and the full analysis set. The analysis for the per-protocol set will be regarded as primary.
 
		

Name of Sponsor: Abbott	Name of Finished Product: Itopride Hydrochloride 150mg extended release tablets	Name of Active Ingredient(s): Itopride

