## **Efficacy**

### Primary efficacy:

- An ANCOVA analysis will be performed with the change in the LDQ score as dependent variable and treatment group, site and LDQ baseline value as additional factors. The difference between the two treatment groups will be calculated for the non-inferiority comparisons, together with a two-sided 95% confidence interval. Non-inferiority will be considered achieved if the lower bound of the 95% confidence interval of the difference

---

between the two groups is greater than 1.75 (NI-margin). Normal approximation will be assumed for the parametric analyses. The primary analysis will be performed for both the per protocol set and the full analysis set. The analysis for the per-protocol set will be regarded as primary.

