#### **10.7 Determination of Sample Size**

Assumptions for sample size calculation are based on the studies of Holtmann et al. and Talley et al. from which a standard deviation of 7 can be assumed for the change of the LD questionnaire.

For the NI margin following assumptions were made:

- In the Holtmann study a difference to placebo 2 (95% CI: 0.03-3.97) in the LDQ was reported.
- In the Ang publication (2011) a difference of 10-15% to placebo is regarded as clinically relevant
- NI-margin needs to be lower than 2. A difference of 15% results in 1.74. Therefore, a NI margin of 1.75 is chosen.

---

Assuming a NI margin of 1.75 and standard deviation of 7 for the change in the LDQ severity score, 253 subjects per treatment arm are required to conclude non-inferiority between the 2 treatment groups with a power of 80% at  $\alpha$ -level of 2.5% single sided. Adding a 10% drop-out rate the total sample size would be 564 subjects (N= 282 per arm).

---

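### The primary success rule pairs the lower confidence bound with +1.75, which is not a non-inferiority test under any coding of the LDQ difference

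*SAP*

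**What the plan says.** SAP section 4.2.1 makes one rule decide whether the trial succeeds: the "lower bound of the 95% confidence interval of the difference between the Test groups and Active Control group is greater than 1.75". The protocol has the same rule in the synopsis (Statistical Methods), where the test is whether the "lower bound of the 95% confidence interval of the difference between the two groups is greater than 1.75 (NI-margin" value, and again under Primary efficacy in section 10.2. None of the three has a minus sign. SAP section 7.1, which lists departures from the protocol analysis, does not alter the rule.

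The analysed variable is identified only by a code comment, "CHG: LDQ change from baseline values", and by verbal definitions of the mean change in each arm. SAP section 5.3.1 scores each LDQ item upward from very mild to very severe. SAP section 5.3.2 counts a patient as an LDQ responder when the final total is below 9. Lower is therefore better.

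Protocol section 10.7 sizes the trial as an ordinary non-inferiority comparison: "Assuming a NI margin of 1.75 and standard deviation of 7 for the change in the LDQ severity score", at a "level of 2.5% single sided", with 80% power and 253 per arm.

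**The concern.** A non-inferiority rule must exclude the possibility that Test is worse than Control by the margin or more. Which bound does this depends on the sign convention:

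- **Change = week 8 minus baseline, difference = Test minus Control.** Improvement is negative and a positive difference means Test is worse. The rule must be upper bound < +1.75. The written rule is met only when Test is shown to be worse by more than the margin.
- **Coding in which positive favours Test.** The rule must be lower bound > −1.75. The written rule instead demands superiority by more than 1.75 points.

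No convention makes the written rule a non-inferiority test. Applied literally, it either reverses the conclusion or makes success practically unattainable, and the stated 80% power does not belong to it. If it were reinterpreted after the results were known, the sponsor would be changing its primary criterion post hoc in an open-label trial.

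**Working it through.** **Inputs.** Margin 1.75, SD 7, 253 per arm, one-sided 2.5%, 80% power, 10% dropout (protocol section 10.7); 1:1 allocation (section 4.1). The documents state no true difference for the sample size; zero is assumed because it reproduces the plan's figure.

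**Reproducing the sample size.** n = 2 × [7 × (1.960 + 0.842) / 1.75]² = 251.2, so 252 per arm by the normal formula. With the t distribution, power is 0.7998 at 252 and 0.8014 at 253, which gives the plan's 253. Dropout: 253 / 0.9 = 281.1, so 282 per arm and 564 in total. The plan's figures are those of a standard non-inferiority test.

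**Precision.** SE = 7 × √(2/253) = 0.622. The 95% half-width is 1.96 × 0.622 = 1.22. The written rule therefore needs an observed difference above 1.75 + 1.22 = 2.97. The correct rule on Test minus Control needs an observed difference below 1.75 − 1.22 = 0.53.

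**Probability of declaring non-inferiority** at true difference d (week 8 minus baseline, Test minus Control, positive = Test worse):

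- Written rule: 1 − Φ[(1.75 − d)/SE + 1.96]
- Correct rule: Φ[(1.75 − d)/SE − 1.96]

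| d | Written rule (lower > 1.75) | Correct rule (upper < 1.75) |
|---|---|---|
| 0 | 0.0000009 | 80.3% |
| 1.75 | 2.5% | 2.5% |
| 2 | 6.0% | 0.9% |
| 2.5 | 22.5% | 0.08% |
| 3 | 51.9% | <0.01% |
| 3.5 | 80.3% | <0.01% |
| 4 | 95.1% | <0.01% |

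Worked examples for the written rule: at d = 0, P(Z > 2.97/0.622 = 4.77) = 9.1 × 10⁻⁷; at d = 4, P(Z > (2.97 − 4)/0.622 = −1.655) = 0.951.

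**Sensitivity.** With 282 per arm the written rule succeeds at d = 0 with probability 4.1 × 10⁻⁷, and the correct rule has 84.3% power. For assumed SDs from 5 to 9 with 253 per arm, the written rule's success at d = 0 lies between 1.9 × 10⁻⁹ and 1.7 × 10⁻⁵. Its success at d = 3.5 runs from 98% down to 59%.

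**Related output.** The sample code in SAP section 4.2.1 does not fix the direction of the treatment contrast, so the sign of the printed difference depends on how the arms are coded. The p-value in the shell for Table 10.1.2.1.1.1 comes from the same ANCOVA and tests a difference of zero, not the margin.

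**The case against.** The intent is plain: the hypotheses are stated in words and the sample size fits only the ordinary rule, so this is a drafting slip. The slip may also be smaller than it looks. Protocol section 10.7 reports itopride's advantage over placebo as a positive number (2, 95% CI 0.03 to 3.97). If positive favours Test throughout, the lower bound is the right one and only a minus sign is missing. The rule is then too strict and could not pass a worse product. A 4-point deficit is also an extreme scenario: it is twice the reported placebo difference, for two regimens that protocol section 7.5 describes as bioequivalent in extent of exposure. A formula defining the contrast may have been lost from the text available for review. The shell p-value plays no part in the decision.

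Much of this stands. The risk of passing a worse product does depend on the coding. At a deficit of 2 points the chance is about 6%, not 95%. The absence of a hypothesis formula is not counted against the plan, and the p-value is a minor matter.

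What it does not do is rescue the rule. The prose is wrong in all three places under either coding, and the near-zero chance of success at true equality is the same under both. The more natural reading of change from baseline is week 8 minus baseline. The −2 threshold in the NRS-11 responder definition (SAP section 5.3.2) supports it, although the shell for Table 10.1.2.2.5.1 prints that threshold without the minus.

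**Conclusion.** The concern holds and must be fixed. As written, the sole success criterion is not a non-inferiority test. Taking SD 7, 253 per arm and a normal approximation, an equivalent product would meet it with probability about 9 × 10⁻⁷ whatever the sign convention. The correct rule gives 80.3% power at equality and a 2.5% false-success rate at the margin, which are the operating characteristics the plan claims.

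The second consequence is conditional. Only with change as week 8 minus baseline and difference as Test minus Control would a worse product be declared non-inferior (22.5% at 2.5 points worse, 95.1% at 4 points worse). Under the opposite coding the written rule requires superiority by more than 1.75. The observed advantage over active itopride would then have to exceed 2.97, more than the 2 points that protocol section 10.7 reports for itopride over placebo.

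**What to change.** In the protocol synopsis, protocol section 10.2 and SAP section 4.2.1, state one convention in full:

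- change = week 8 minus baseline, negative meaning improvement;
- difference = LS mean Test minus LS mean Control;
- H0: difference ≥ 1.75 against H1: difference < 1.75;
- non-inferiority is concluded if the **upper** limit of the two-sided 95% confidence interval is below 1.75.

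Coding improvement as positive and requiring the lower limit above −1.75 is equivalent. Make one change or the other, not both: upper limit below −1.75 would be a superiority test.

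Fix the contrast direction explicitly in the SAP code, including the step that pools the imputed results. In the primary table shells, replace the zero-difference p-value with a one-sided p-value against the margin, or delete it.

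The cost is a correction to the rule in three places, short definitions, and edits to the code and shells. Data collection and sample size are unaffected. Because the protocol's success criterion changes, the sponsor should expect it to count as a substantial amendment under protocol section 12.1, needing ethics committee approval. It should be completed before database lock.
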